APPENDIX H: WORLD ALLERGY ORGANIZATION GRADING SYSTEM

Table 9. World Allergy Organization Subcutaneous Immunotherapy Systemic Reaction Grading System

Grade 1	Grade 2	Grade 3	Grade 4	Grade 5

Symptom(s)/sign(s) of one organ system presentⁱ
 
Cutaneous
 
Generalized pruritus, urticaria, flushing or sensation of heat or warmthⁱⁱ
 
or
 
Angioedema (not laryngeal, tongue or uvular)
 
or
 
Upper respiratory
 
Rhinitis (e.g., sneezing, rhinorrhea, nasal pruritus and/or nasal congestion)
 
or
 
Throat-clearing (itchy throat)
 
or
 
Cough perceived to come from the upper airway, not the lung, larynx, or trachea
 
or
 
Conjunctival
 
Conjunctival erythema, pruritus or tearing
 
Other
 
Nausea, metallic taste, or headache
	
Symptom(s)/sign(s) of more than one organ system present
 
or
 
Lower respiratory
 
Asthma: cough, wheezing, shortness of breath (e.g., less than 40% PEF or FEV1 drop, responding to an inhaled bronchodilator)
 
or
 
Gastrointestinal
 
Abdominal cramps, vomiting, or diarrhea
 
or
 
Other
 
Uterine cramps
	
Lower respiratory
 
Asthma (e.g., 40% PEF or FEV1 drop, NOT responding to an inhaled bronchodilator)
 
or
 
Upper respiratory
 
Laryngeal, uvula or tongue edema with or without stridor
	
Lower or Upper respiratory
 
Respiratory failure with or without loss of consciousness
 
or
 
Cardiovascular
 
Hypotension with or without loss of consciousness
	
Death

Table 9. World Allergy Organization Subcutaneous Immunotherapy Systemic Reaction Grading System (Continued)

Patients may also have a feeling of impending doom, especially in grades 2, 3, or 4.
 
Note: children with anaphylaxis seldom convey a sense of impending doom and their behavior changes may be a sign of anaphylaxis, e.g., becoming very quiet or irritable and cranky.

Scoring includes a suffix that denotes if and when epinephrine is or is not administered in relationship to symptom(s)/sign(s) of the SR: a, ≤ 5 minutes; b, >5 minutes to ≤ 10 minutes; c, >10 to ≤ 20 minutes; d, >20 minutes; z, epinephrine not administered.


The final grade of the reaction will not be determined until the event is over, regardless of the medication administered. The final report should include the first symptom(s)/sign(s) and the time of onset after the subcutaneous allergen immunotherapy injection ⁱⁱ and a suffix reflecting if and when epinephrine was or was not administered, e.g., Grade 2a; rhinitis:10 minutes.

Final report: Grade a-d, or z _____ First symptom _____ Time of onset of first symptom _____

Comments^{iv}

- i. Each Grade is based on organ system involved and severity. Organ systems are defined as: cutaneous, conjunctival, upper respiratory, lower respiratory, gastrointestinal, cardiovascular and other. A reaction from a single organ system such as cutaneous, conjunctival, or upper respiratory, but not asthma, gastrointestinal, or cardiovascular is classified as a Grade 1. Symptom(s)/sign(s) from more than one organ system or asthma, gastrointestinal, or cardiovascular are classified as Grades 2 or 3. Respiratory failure or hypotension, with or without loss of consciousness, defines Grade 4 and death Grade 5. The Grade is determined by the physician's clinical judgment.
- ii. This constellation of symptoms may rapidly progress to a more severe reaction.
- iii. Symptoms occurring within the first minutes after the injection may be a sign of severe anaphylaxis. Mild symptoms may progress rapidly to severe anaphylaxis and death.
- iv. If signs or symptoms are not included in the Table or the differentiation between an SR and vasovagal (vasodepressor) reaction, which may occur with any medical intervention, is difficult, please include comment, as appropriate.

provided with permission from Cox L, Larenas-Linnemann D, Lockey RF, et al. J Allergy Clin Immunol 125:569-574, e567; reprinted with permission from Elsevier Inc)

APPENDIX I: CENTRAL LABORATORY REFERENCE RANGES

Reference Ranges, Notable Values, Critical Values, and Methodology

Sponsor: ENYO Pharma SA
Protocol: EYP001-202

[name] *20 May 2019*
Lab Director Date (dd/MMM/yyyy)

Test Name	Subject Characteristics	Unit	Reference Range	Notable Values	Critical Values	Methodology
Chemistry						
Alkaline Phosphatase	Adult	U/L	41 - 146	> 348	---	Photometry
ALT/SGPT	Adult	U/L	10 - 53	> 123	> 164	Photometry
AST/SGOT	Adult	U/L	14 - 43	> 102	> 136	Photometry
Bilirubin (Direct)	Adult	µmol/L	0.0 - 3.4	---	---	Photometry
Bilirubin (Total)	Adult	µmol/L	1.7 - 18.8	> 34.2	---	Photometry
Gamma Glutamyl Transferase (GGT)	Adult Male	U/L	11 - 52	> 156	---	Photometry
	Adult Female	U/L	7 - 38	> 114	---	
Coagulation						
International Normalized Ratio (INR)	All	(None)	0.8 - 1.2	---	> 2.5	Calculation
Hematology						
Platelet	Adult	10 ⁹ /L	140 - 400	---	< 40 or > 999	Impedance

Reference Ranges, Notable Values, Critical Values, and Methodology

Sponsor: ENYO Pharma SA

Protocol: EYP001-202

[name] *20/01/2015*
Lab Director Date(dd/mm/yy)

Test Name	Subject Characteristics	Unit	Reference Range	Notable Values	Critical Values	Methodology
Chemistry						
Alkaline Phosphatase	Adult	U/L	41 - 146	> 348	---	Photometry
ALT/SGPT	Adult	U/L	10 - 53	> 123	> 164	Photometry
AST/SGOT	Adult	U/L	14 - 43	> 102	> 136	Photometry
Bilirubin (Direct)	Adult	mg/dL	0.00 - 0.20	---	---	Photometry
Bilirubin (Total)	Adult	mg/dL	0.10 - 1.10	> 2.00	---	Photometry
Gamma Glutamyl Transferase (GGT)	Adult Male	U/L	11 - 52	> 156	---	Photometry
	Adult Female	U/L	7 - 38	> 114	---	
Coagulation						
International Normalized Ratio (INR)	All	(None)	0.8 - 1.2	---	> 2.5	Calculation
Hematology						
Platelet	Adult	10 ³ /µL	140 - 400	---	< 40 or > 999	Impedance

cT1	Iron-corrected T1
DBP	Diastolic blood pressure
DSMC	Data Safety Monitoring Committee
ECG	Electrocardiogram
eCRF	Electronic case report forms
ELF	Enhanced liver fibrosis
ET	Early termination
FIB-4	Fibrosis-4
GGT	Gamma-glutamyltransferase
HbA1c	Hemoglobin A1c
hs-CRP	High sensitivity C-reactive protein
HR	Heart rate
INR	International normalized ratio
IRT	Interactive Response Technology
ITT	Intent-to-treat
LDL	Low-density lipoprotein
LFC	Liver fat content
LLN	Lower limit of normal
LSM	Liver stiffness measurement
LSMean	Least square means
MAR	Missing at random
MCMC	Markov Chain Monte Carlo
MedDRA	Medical Dictionary for Regulatory Activities
mITT	Modified intent-to-treat
MMRM	Mixed-model repeated measures
MRI-PDFF	Magnetic resonance imaging-proton density fat fraction
NAFLD	Nonalcoholic fatty liver disease
NASH	Nonalcoholic steatohepatitis
PD	Pharmacodynamics

Abbreviation	Definition
PK	Pharmacokinetics
QD	Once daily
SAE	Serious adverse event
SAP	Statistical Analysis Plan
SBP	Systolic blood pressure
SDTM	Study Data Tabulation Model
T2DM	Type 2 diabetes mellitus
TEAE	Treatment-emergent adverse event
TESAE	Treatment-emergent serious adverse event
TFLs	Tables, figures, and listings
ULN	Upper limit of normal
VAS	Visual analog scale
VLDL	Very low-density lipoprotein
WHO	World Health Organization

1 INTRODUCTION

The purpose of this Statistical Analysis Plan (SAP) is to provide a description of the statistical methods to be implemented for the analysis of data from the study with protocol number EYP001-202. The SAP will be finalized prior to the first database lock. Any deviations from the SAP after final database lock will be documented in the final Clinical Study Report (CSR).

This SAP covers both Part A and Part B of the study with a focus on what is needed for analysis of Part B. Refer to the SAP V1.0 for what was used to perform the analysis of Part A. Unless otherwise specified, the analyses of Part A and Part B will be performed separately.

2 STUDY OVERVIEW

2.1 Study Objectives and Endpoints

2.1.1 Primary Objective and Endpoint

Primary Objective	Endpoint
The primary objective is to determine the efficacy and safety profiles of EYP001a versus placebo on liver fat content (LFC) from baseline to Week 12 in patients with nonalcoholic steatohepatitis (NASH).	
The primary efficacy variable is absolute change in LFC as measured by magnetic resonance imaging-proton density fat fraction (MRI-PDFF) from baseline to Week 12/Early Termination (ET).
 
The secondary efficacy variables include the following:
 
• Proportion of patients with $\geq 5\%$ absolute reduction in LFC as measured by MRI-PDFF from baseline to Week 12/ET• Proportion of patients with $\geq 10\%$ absolute reduction in LFC as measured by MRI-PDFF at Week 12/ET• Proportion of patients with $\geq 20\%$ absolute reduction in LFC as measured by MRI-PDFF at Week 12/ET• Proportion of patients with a relative reduction in LFC $\geq 20\%$ as measured by MRI-PDFF at Week 12/ET• Proportion of patients with a relative reduction in LFC $\geq 30\%$ as measured by MRI-PDFF at Week 12/ET• Percent change (relative reduction) in LFC as measured by MRI-PDFF from baseline to Week 12/ET

2.1.2 Secondary Objectives and Endpoints

Secondary Objective	Endpoint
To explore the pharmacokinetics (PK) of EYP001a	EYP001a concentrations
To evaluate pharmacodynamic (PD) effects of EYP001a on bile acid-related markers as appropriate	Plasma levels of: 
• 7a-hydroxy-4-cholest-3-one;• fibroblast growth factor 19;• and total, primary, and secondary bile acids (such as
◦ chenodeoxycholic acid,◦ deoxycholic acid,◦ lithocholic acid,◦ and/or others as appropriate).
To assess the effects of EYP001a on lipid and metabolic profiles	
• Branched-chain amino acid concentrations• Hemoglobin A1c (HbA1c)• Homeostatic model assessment for insulin resistance (morning fasting glucose and insulin)• Lipoprotein insulin resistance index by nuclear magnetic resonance based on serum
◦ cholesterol,◦ high-density lipoprotein cholesterol,◦ low-density lipoprotein (LDL) cholesterol,◦ triglycerides,◦ apolipoprotein B,◦ small dense-LDL, and◦ lipoprotein(a)• Lipoprotein particle size• Small LDL particle number• Small very low-density lipoprotein (VLDL) particle number• VLDL size
To assess the safety of EYP001a with statin coadministration	Safety and tolerability assessments will include the monitoring of

Secondary Objective	Endpoint
	
adverse events (AEs);AEs of special interest (AESIs) (i.e.,
pruritus [Part A only],drug-induced liver injury [Part A only],elevation of transaminases [Part B only],andall muscle-related AEs);serious AEs (SAEs); and findings fromphysical examinations,vital signs,electrocardiograms (ECGs), andclinical laboratory parameters.
To assess the effects of EYP001a on noninvasive biomarkers of liver fibrosis and inflammation	
Change from baseline to Week 4, Week 8, and Week 14/ET, as applicable, in the following biomarkers of liver fibrosis and inflammation:
 
Alanine aminotransferase (ALT),Aspartate aminotransferase (AST),AST/ALT ratio,adiponectin,high sensitivity C-reactive protein (hs-CRP),interleukin 6,tumor necrosis factor alpha,cytokeratin-18,fibronectin,hyaluronic acid,procollagen type III N-terminal peptide,tissue inhibitor of metalloproteinases-1 (and derived enhanced liver fibrosis [ELF] score),Pro-C3, andchitinase-3-like protein 1 (also known as YKL-40)

Additional secondary efficacy variables include the following:

[figure not shown]
- Change and percent change in imaging-derived mean iron-corrected T1 (cT1) from baseline to Week 12
- Change and percent change in body mass index (BMI), waist circumference, and body weight
- Change and percent change in waist to hip ratio from baseline to Week 12 (Part B only)
- Change and percent change in waist to height ratio from baseline to Week 12 (Part B only)
- Derived non-invasive biomarkers of liver fibrosis and inflammation:
 - AST to platelet ratio index
 - Bile acid-CoA:amino acid N-acyltransferase (BAAT) Score
 - BMI-AST/ALT Ratio-Diabetes (BARD) Score
 - Nonalcoholic Fatty Liver Disease (NAFLD) Fibrosis Score
 - Fibrosis-4 (FIB-4) Score

2.2 Study Design

2.2.1 Overview

This is a 2-part, randomized, double-blind, multicenter, placebo-controlled study to evaluate the safety and efficacy of EYP001a in patients with NASH who likely have stage F2 to F3 fibrosis at approximately 50 global clinical sites. Overall, approximately 114 eligible patients will be enrolled: 24 patients in Part A (Safety Run-in Cohort), followed by 90 patients in Part B. In Part A, 24 patients will be randomized on Day 1 to 1 of 4 parallel treatment groups: 100 mg EYP001a twice daily (BID), 200 mg EYP001a once daily (QD), 400 mg EYP001a QD, or placebo BID. In Part B, 90 patients will be randomized on Day 1 to 1 of 3 parallel treatment groups: 100 mg EYP001a QD, 200 mg EYP001a QD, or placebo QD.

Randomization will be stratified by statin use (yes, no) and type 2 diabetes mellitus (T2DM) status (yes, no) at screening in Part A, and by statin use (yes, no) and LFC (stratification factor with 3 categories: LFC<16%, 16%≤LFC<22%, and 22%≤LFC) in Part B at screening.

BID = twice daily; D = Day; DSMC = Data Safety Monitoring Committee; QD = once daily; Wk = Week.

2.2.2 Randomization and Blinding

This study follows a randomized, double-blind, placebo-controlled design. Patients in Part A will be randomized via the Interactive Response Technology (IRT) system to 1 of 4 parallel treatment groups on Day 1 in a 1:1:1:1 ratio. However, prerandomization will occur within the IRT system at least 7 days prior to randomization. Patients in Part B will be randomized via the IRT system to 1 of 3 parallel treatment groups on Day 1 in a 1:1:1 ratio. Prerandomization is not applicable in Part B.

Both EYP001a and placebo will be provided as tablets for oral administration and will be identical in appearance.

Prerandomization/randomization information will be concealed from the Investigators and the patients until the end of the study, with the exception of an emergency situation involving a patient that required unblinding of the treatment assignment.

Stratification

Randomization will be stratified by statin use (yes, no) and T2DM status (yes, no) in Part A, and by statin use (yes, no) and LFC (stratification factor with 3 categories: LFC<16%, 16%≤LFC<22%, and 22%≤LFC) in Part B at screening. Randomization can occur after eligibility check on Day -3, at the earliest, and prior to dosing on Day 1 at the latest.

2.2.3 Study Drug

Formulation and Packaging

The drug product will be supplied as immediate-release coated tablets for oral administration. Excipients include lactose monohydrate, microcrystalline cellulose, crospovidone, sodium lauryl sulfate, silicon dioxide, and magnesium stearate. Placebo tablets will appear identical to EYP001a.

For Part A, all study drug (EYP001a and placebo) will be packaged in blister packs and wallets. One wallet will contain 2 weeks of study drug (i.e., 14 days of EYP001a or placebo) as per the randomization schedule. Morning and evening tablets will be clearly labeled.

For Part B, all study drug (EYP001a and placebo) will be packaged in blister packs and carton boxes. One box will contain 3 weeks of study drug (i.e., 3 blister strips or 21 days of EYP001a or placebo) as per the randomization schedule.

Study Drug Preparation and Dispensing

For Part A, study drug will be dispensed as 100 and 200 mg tablets for oral administration at Weeks 0, 2, 4, and 8 by blinded clinical site personnel. Patients will receive enough study drug to last until the next visit.

For Part B, study drug will be dispensed as 100 and 200 mg tablets for oral administration at Weeks 0, 2, 4, 6, 8, and 10 by blinded clinical site personnel. Patients will receive enough study drug to last until the next visit.

Study Drug Administration

EYP001a is only available for oral administration. The study drug should be administered with noncarbonated water.

For Part A, patients will take 2 tablets in the morning during breakfast and 1 tablet in the evening during dinner.

For Part B, patients will take 1 tablet in the morning during breakfast. On study visit days, patients should come fasted to the clinical site and take their morning dose during breakfast at the clinical site, following blood sample collection, except during intense PK/PD sampling on Days 1 and 14 of Part A, when dosing will occur with water only.

2.2.4 Sample Size Determination

The sample size of 114 randomized patients (n = 24 patients in Part A and n = 90 in Part B [n = 30 patients per treatment group]) is based on the efficacy endpoint: absolute change in LFC as measured by MRI-PDFF from baseline to Week 12, assuming that the treatment difference between each active treatment group with placebo is at least 5.1% with a common standard deviation of 5.8%.

With a 2-sample Z-test with the power of 0.8 and an overall family-wise 1-sided alpha of 0.025 (or *each.active*.*versus.placebo*.*alpha* = 0.0125 after Bonferroni adjustment), 26 patients per treatment group will be needed to complete the Week 12 Visit. With the consideration of an approximately 13% dropout rate before Week 12, 30 patients will be randomized per treatment group in Part B.

3 STATISTICAL METHODOLOGY

3.1 General Considerations

3.1.1 Treatment Groups

Data will be summarized and listed according to the randomized or actual treatment group, as appropriate.

In addition for Part A, data from the EYP001a treatment groups will be pooled and summarized. For analysis, due to the small number of patients by treatment group and as the PK results between group were found to be non-linear, with similar exposure for the EYP001a 200 mg QD and EYP001a 400 mg QD groups, only the pooled EYP001a treatment group will be compared with placebo.

In Part B, treatment groups will be summarized and analyzed separately. The EYP001a treatment groups will not be pooled.

3.1.2 Analysis Day

Analysis day will be calculated from the date of first dose of study drug. The day of the first dose of study drug will be Day 1, and the day immediately before Day 1 will be Day -1. There will be no Day 0.

Analysis Day will be calculated as:

Date of assessment – date of first dose of study drug
+ 1 (*if date of assessment ≥ date of first dose of study drug*)

3.1.3 Definition of Baseline

Baseline for the imaging parameters (LFC, cT1, liver stiffness measurement [LSM] and controlled attenuation parameter [CAP]) will be defined as the value obtained at the Screening Visit.

Baseline for ALT, AST, Total Bilirubin and alkaline phosphatase (ALP) will be defined as the average of all pre-dose values (i.e. those taken during the Screening Period and on Day 1 as assessed by the central laboratory). Only assessments taken within 12 weeks prior to Day 1 will be considered in the average calculation.

Baseline for the AST/ALT Ratio will be calculated using the derived baseline values for ALT and AST as described above.

Baseline for the other efficacy and safety variables will be defined as the last available value obtained up to the first dose of study drug.

For patients randomized and not treated, the baseline value will be the last available value on or before the day of randomization.

3.1.4 Analysis Visits

Refer to SAP V1.0 for Part A analysis visits.

Part B

For LFC, cT1, LSM and CAP, analysis visits will be assigned according to the labelled visit. I.e. "Baseline" analysis visit will be sourced from the "Screening" visit, and "Week 12/ET" analysis visit will be sourced from the "Week 12" or "ET" visit. Note that the ET assessment will be performed only for patients on study drug for ≥4 weeks.

For all other efficacy assessments with regular scheduled visits, analysis visits will be assigned according to the labelled visit. In addition to maximize the data available for assessments with regular scheduled visits, where possible, results from ET and unscheduled visits will be allocated to a post-baseline scheduled visit according to the following rules and visit windows

described in the table below (defined as the halfway point between the target visit days). If a valid value exists for the scheduled visit to which the ET/unscheduled visit has been allocated then the value from the scheduled visit will be used in the analysis, otherwise the values from the ET/unscheduled visits will be used in the analysis for the particular scheduled visit. If there is more than one assessment within a visit window, then the analysis visit will be assigned by the following priorities:

1. Use the assessment from the visit with the matching visit label.
2. Use the visit closest to the target visit day; in the case of ties, use the earlier visit.

Analysis Visit and Target Analysis Day	Visit Windows (Analysis Days)		
	Group I	Group II	Group III
Baseline	See Section 3.1.3		
Day 14 (Week 2)	2 – 21	2 – 21	
Day 28 (Week 4)	22 – 35	22 – 42	2 – 42
Day 42 (Week 6)	36 – 49		
Day 56 (Week 8)	50 – 61	43 – 70	43 – 77
Day 70 (Week 10)	62 – 77		
Day 84 (Week 12)	78 – 91	71 – 91	
Day 98 (Week 14) EOS FUP	92+	92+	92+
Group I: ALT, AST, AST/ALT Ratio, ALP, Total Bilirubin, Gamma-glutamyltransferase (GGT)			
Group II: hs-CRP, CK, BMI, Waist Circumference, Body Weight, Waist to Height Ratio, Waist to Hip Ratio, and lipids and metabolic profile			
Group III: HbA1c and all other biomarkers of liver fibrosis and inflammation			

Note that parameters that are considered both efficacy and safety (ALT, AST, CK) will use analysis visit windowing for both the efficacy and safety summaries and analyses for Part A and Part B.

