6.5 Early Termination Visit and Withdrawal Procedures (Parts A and B)

The end of treatment for patients completing the study is Day 84 (Week 12).

Patients who discontinue early from the study for any reason before completion of the Treatment Period will be requested to return to the clinic for an ET Visit within a maximum of 48 hours after their last intake of study drug, regardless of how many days they participated in the study.

Patients who discontinue early from the study for any reason after completion of the Treatment Period and before the EOS Follow-up Visit will be requested to return to the clinic for an ET Visit as soon as possible and no later than the planned EOS Follow-up Visit.

For patients who are withdrawn from the study prior to completion, all ET procedures will be performed at an ET Visit. These procedures include the following:

- Record changes in concomitant medications.
- Perform brief physical examination.
- Measure body weight and calculate BMI.
- Measure waist circumference (Part A only).
- Measure waist and hip circumferences (Part B only).
- Calculate WHR and WHtR (Part B only).
- Collect vital signs (systolic and diastolic blood pressure, heart rate, respiratory rate, and body temperature) with the patient in the sitting position after 5 minutes of rest and before any blood draws.
- Administer the AUDIT-C test.
- Counsel on diet/lifestyle.
- Collect blood sample for the following:
 - Chemistry, hematology, coagulation, and lipid and metabolic profile.
 - PD (preferably within 24 to 48 hours of last intake of study drug).
 - Liver fibrosis and inflammation.
 - Serum pregnancy test.

- PK (preferably within 24 to 48 hours of last intake of study drug).
- Plasma storage.
- Collect urine sample for urinalysis.
- Perform 12-lead ECG.
- Perform MRI-PDFF and cT1 imaging only for patients on study drug ≥ 4 weeks.
- Perform FibroScan VCTE (optional).
- Assess pruritus (Part A only).
- Assess adverse events.
- Collect returned used/unused study drug and assess compliance.

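### SAP 3.1.4 (Part B): two visit windows depart from the stated halfway rule, leaving Group III Days 78-91 without an analysis visit and sending Group I Days 62-63 to Week 10

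*SAP*

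**What the plan says.** SAP 3.1.4 assigns scheduled visits by their label. Then, "In addition to maximize the data available for assessments with regular scheduled visits", it adds that, where possible, "results from ET and unscheduled visits will be allocated to a post-baseline scheduled visit according to the following rules and visit windows". The windows are "defined as the halfway point between the target visit days". A scheduled value has priority. If there is none, "otherwise the values from the ET/unscheduled visits will be used in the analysis for the particular scheduled visit". When several assessments fall in one window, the matching label comes first, and after that: "Use the visit closest to the target visit day; in the case of ties, use the earlier visit".

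The Part B table has three groups:

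- Group I: ALT, AST, AST/ALT ratio, ALP, total bilirubin and GGT.
- Group II: hs-CRP, CK, anthropometrics, and the lipid and metabolic profile.
- "Group III: HbA1c and all other biomarkers of liver fibrosis and inflammation".

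For the biomarkers, SAP 2.1.2 defines the endpoint as "Change from baseline to Week 4, Week 8, and Week 14/ET, as applicable". SAP Section 5 says that HbA1c is not analysed at Weeks 2 and 12. Neither 3.1.4 nor Section 5 states an exception to the halfway rule.

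Protocol 6.5 includes the fibrosis and inflammation panel in the ET visit. A patient who stops during treatment returns within 48 hours of the last dose. One who leaves after treatment but before follow-up "will be requested to return to the clinic for an ET Visit as soon as possible and no later than the planned EOS Follow-up Visit". Protocol 6.3.3.7 does not list the panel at Day 84.

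**The concern.** The windows exist to recover ET and unscheduled results, so a gap or a misplaced cut works against their purpose.

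**Group III.** The panel is not drawn at Week 12. For a patient who leaves near or just after the end of treatment, the ET sample may be the only one after Week 8. Both ET routes in Protocol 6.5 can produce a sample on Days 78-91. The endpoint counts ET samples by name, yet the table gives them no visit. They would be missing from the by-visit summaries and from the biomarker MMRM in SAP 3.4.2.1.

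**Group I.** A Day 62 result is nearer to Week 8 but is filed under Week 10. If the scheduled Week 10 value is missing, the Day 62 result fills that cell. If the scheduled Week 8 value is missing, the result is not available to fill it. SAP 3.1.4 applies the ALT and AST windows to both the efficacy and the safety summaries.

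**Working it through.** **Inputs.** Target days and windows come from the SAP 3.1.4 table. The rule is: cut = (earlier target + later target) / 2.

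**Which side gets the midpoint day?** Group II settles the convention. Its targets are 14, 28, 56, 84 and 98, and its midpoints are (14+28)/2 = 21, (28+56)/2 = 42, (56+84)/2 = 70 and (84+98)/2 = 91. The table gives 2-21, 22-42, 43-70, 71-91 and 92+. All five windows are reproduced if the midpoint day goes to the earlier visit. If it goes to the later visit, no window in any group is reproduced.

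**Group I** (targets 14, 28, 42, 56, 70, 84, 98)

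| Pair | Midpoint | Table cut | Agrees |
|---|---|---|---|
| 14/28 | 21 | 21/22 | yes |
| 28/42 | 35 | 35/36 | yes |
| 42/56 | 49 | 49/50 | yes |
| 56/70 | 63 | 61/62 | **no** |
| 70/84 | 77 | 77/78 | yes |
| 84/98 | 91 | 91/92 | yes |

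Five of the seven windows are reproduced. The two that meet at the wrong cut should be 50-63 and 64-77.

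- Day 62 is 62 - 56 = 6 days from Week 8 and 70 - 62 = 8 days from Week 10, yet it goes to Week 10. It is the only day in the table sent to a strictly farther target.
- Day 63 is 7 days from each. The rule alone does not place it. The convention shown above places it in Week 8.

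**Group III** (targets 28, 56, 98)

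| Pair | Midpoint | Earlier window ends | Later window starts | Agrees |
|---|---|---|---|---|
| 28/56 | 42 | 42 | 43 | yes |
| 56/98 | 77 | 77 | 92 | **no** |

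Two of the three windows are reproduced. Week 14 should start at Day 78. The printed start of 92 follows the 84/98 midpoint (91) used in Groups I and II, but Group III has no Day 84 window. The unassigned span is 91 - 78 + 1 = 14 days. Each of those days is nearer to Day 98 than to Day 56: Day 78 is 20 against 22 days away, and Day 91 is 7 against 35. Groups I and II leave no day unassigned.

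**Is the blank Week 12 cell a table-reading loss?** No. With a Day 84 target, Group III Week 8 would end at (56+84)/2 = 70, as in Group II. It ends at 77.

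**The case against.** **The Group III gap may be deliberate.** Days 78-91 are exactly Group I's Week 12 window, and 77 is also the 70/84 midpoint. HbA1c is drawn on Day 84 with the metabolic profile but is not analysed at Week 12, which fits an empty cell. Allocation is also promised only where possible. A blank would keep samples taken on or just after treatment out of an off-treatment follow-up visit. This is a fair reading, but the SAP does not state it. It would also discard ET samples taken after treatment ends, on about Days 85-91, and it sits badly with an endpoint defined at Week 14/ET.

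**Section 5 adds Week 12 for the fibrosis and inflammation biomarkers, as appropriate.** This fits markers that have a Week 12 window, such as ALT, AST and hs-CRP. It does not give Group III such a window.

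A reader might also infer more than the documents support:

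- *That the SAP's tie rule puts Day 63 in Week 8.* That rule chooses between assessments competing within one window. It does not place one result lying midway between two targets. Day 63 rests on the table's convention only.
- *That all fibrosis markers are affected.* ALT, AST, the AST/ALT ratio and hs-CRP are on the biomarker list but sit in Groups I and II, which have no gap.
- *That repeat liver tests after a Week 8 elevation are misfiled and a signal is hidden.* Such a repeat presupposes a valid scheduled Week 8 value, which has priority even under a 50-63 window. The liver shift tables in SAP 3.7.3 use the maximum post-baseline value, and the monitoring plan in Protocol Appendix E acts on actual results.
- *That data disappear.* SAP 3.4 lists all efficacy data. The loss is from by-visit analyses.

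**Conclusion.** Both departures are confirmed. As written, the table does not follow the rule that introduces it.

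- **Group I:** one day (62) strictly breaks the rule, and one tied day (63) departs from the table's own convention.
- **Group III:** 14 days (78-91) have no analysis visit, for HbA1c and the biomarkers outside Groups I and II.

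The effect is confined to ET and unscheduled results, and to cases where the scheduled visit has no valid value. The documents give no frequency for such cases, so the number of patients cannot be calculated. LFC and cT1 are assigned by visit label and do not use these windows.

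The conclusion assumes that the halfway rule is meant to hold throughout, since no exception is stated. This is a minor point, worth correcting because the correction is nearly free.

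**What to change.** In the SAP 3.1.4 Part B table:

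- **Group I:** change Week 8 to 50-63 and Week 10 to 64-77.
- **Group III:** start Week 14 at Day 78.

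That is three numbers in one table. Scheduled Day 84 HbA1c samples stay under their Week 12 label, because only ET and unscheduled results are windowed.

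There is one small cost. ET samples from about Days 78-84, taken within 48 hours of the last dose, would be pooled with the off-treatment Week 14 visit. The Week 14/ET endpoint already allows this, and these samples can be flagged.

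Do not add a Week 12 window for HbA1c, because Section 5 excludes that analysis. If the Group III gap was intended, 3.1.4 should say so as an exception and reconcile it with the Week 14/ET endpoint.
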